12.6.2.4 CYP1A2 Activity

CYP1A2 activity will be measured in plasma on Day 0 and Day 5. In this study the CYP1A2 activity will be calculated using the molar ratio of PX and CAF, as described in Section 7.1.4 “CYP1A2”. Descriptive statistics of the values and percent change on Day 5 from Day 0 and supportive listings will be provided.

The analysis will compare the Day 5 values between the THS 2.2 and CC arms and between the THS 2.2 and SA arms. An ANOVA model will be used with terms for sex, average daily CC consumption over the last 4 weeks as reported during screening and product. No adjustment will be made for multiple comparisons.

The SAS code will be the same as described in Section 12.6.1.1 “Primary Biomarkers of Exposure in 24 hour collection”, with no baseline value being included in the model.

LS means for each product along with the difference (THS 2.2 - CC) and 95% CI will be presented in the tables.

CYP1A2 activity will also be examined to compare the observed reductions in THS 2.2 vs. SA using the same methodology as above.

The data will be presented in the below outputs, the TFL number refers to the TFL number in the accompanying TFL shell document:

TFL number	Title
TABLES	
15.2.4.50	Descriptive Statistics of CYP1A2 Activity (%) – FAS
15.2.4.51	Analysis of CYP1A2 Activity (%) on Day 5 to 6 – FAS
LISTINGS	
15.3.4.1	Listing of CYP1A2 Activity and Changes from Baseline

12.6.3 Exploratory Analysis

12.6.3.1 Questionnaires

12.6.3.1.1 Urge-to-Smoke Questionnaire of Smoking Urges Brief

The QSU-brief will be administered daily from Days -1 to 5. The baseline will be the last assessment prior to 06:29 AM on Day 1.

All summaries, profiles and analysis will be presented for the THS 2.2, CC and SA arms.

The change from baseline will be calculated for the total score and the two domain scores (relief and reward). The total score and two domain scores, along with the change from baseline will be summarized. The answers to the individual questions, along with the domain scores, total scores and changes from baseline will be listed.

The profiles of the raw means from baseline to Day 5 for the total score and two domain scores will be produced.

The analysis will compare each post baseline timpoint in the domain and total scores. A repeated measures ANCOVA model will be used with terms for baseline QSU-BRIEF score, sex, average daily CC consumption over the last 4 weeks as reported during screening, product, timepoint, and the interaction between product and timepoint. No adjustment will be made for multiple comparisons.

The SAS code to be used is shown below:

```
Proc mixed data=_data_;
  Class product sex cigarette_cons time_point;
  Model reduction = base_QSU sex cigarette_cons product
  product*time_point;
  Repeated time_point / subject=subject type=un;
  Lsmean product / diff alpha=0.05 cl;
  Run;
```

LS means for each product along with the difference (THS 2.2 - CC) and (THS 2.2 – SA) with 95% CI will be presented in the tables. The SAS code above will also be amended appropriately to obtain the right comparisons.

All figures, summaries and analyses will be performed on the FAS.

The data will be presented in the below outputs, the TFL number refers to the TFL number in the accompanying TFL shell document:

TFL number	Title
FIGURES	
15.1.2.33	QSU-brief Factors and Total Scores Arithmetic Mean and 95% CI – FAS
15.1.2.34	QSU-brief Factors and Total Scores Arithmetic Least Squares Mean Differences and 95% CI – FAS

TFL number	Title
TABLES	
15.2.4.44	Descriptive Statistics of QSU-brief Factors and Total Scores – FAS
15.2.4.45	Analysis of QSU-brief Factors and Total Scores – FAS
LISTINGS	
15.3.6.11	Listing of QSU-brief Questionnaire Results and Changes from Baseline

12.6.3.1.2 Modified Cigarette Evaluation Questionnaire

The MCEQ will be administered daily from Days -1 to 5. The baseline will be the last assessment prior to 06:29 AM on Day 1.

All summaries, profiles and analysis will be presented for the THS 2.2 and CC only. The MCEQ is not captured for the SA arm.

The change from baseline will be calculated for the five domain scores. The domain scores, along with the change from baseline will be summarized. The answers to the individual questions, along with the domain scores and changes from baseline will be listed.

The profiles of the raw means from baseline to Day 5 for the five subscale scores will be produced.

The analysis will compare each post baseline timpoint in the subscales. A repeated measures ANOVA model will be used with terms for baseline MCEQ score, sex, average daily CC consumption over the last 4 weeks as reported during screening, product, time-point, and the interaction between product and time-point. No adjustment will be made for multiple comparisons.

The SAS code will be the same as described in Section 12.6.3.1.1 “Urge-to-Smoke Questionnaire of Smoking Urges Brief”.

LS means for each product along with the difference (THS 2.2 - CC) with 95% CI will be presented in the tables.

All figures, summaries and analyses will be performed on the FAS.

The data will be presented in the below outputs, the TFL number refers to the TFL number in the accompanying TFL shell document:

TFL number	Title
FIGURES	
15.1.2.38	MCEQ Subscales Arithmetic Mean and 95% CI– FAS
15.1.2.39	MCEQ Subscales Arithmetic Least Squares Mean Differences and 95% CI – FAS
TABLES	
15.2.4.48	Descriptive Statistics of MCEQ Subscales – FAS

TFL number	Title
15.2.4.49	Analysis of MCEQ Subscales – FAS
LISTINGS	
15.3.6.13	Listing of MCEQ Questionnaire Results and Changes from Baseline

12.6.3.1.3 Minnesota Nicotine Withdrawal Questionnaire

The MNWS will be administered daily from Days 0 to 6 for the assessment of Day-1 to Day 5 as it is a 24-hour recall questionnaire. The baseline will be the last assessment prior to 06:29 AM on Day 1.

All summaries, profiles and analysis will be presented for the THS 2.2, CC and SA arms.

The change from baseline will be calculated for both scores. The two scores, along with the change from baseline will be summarized. The answers to the individual questions, along with the two scores and changes from baseline will be listed.

The profiles of the raw means from baseline to Day 5 for the total scores will be produced.

The analysis will compare each post baseline timepoint for the two scores. A repeated measures ANCOVA model will be used with terms for baseline score, sex, average daily CC consumption over the last 4 weeks as reported during screening, product, time-point, and the interaction between product and time-point. No adjustment will be made for multiple comparisons.

The SAS code will be the same as described in Section 12.6.3.1.1 “Urge-to-Smoke Questionnaire of Smoking Urges Brief”.

LS means for each product along with the difference (THS 2.2 - CC) and (THS 2.2 – SA) with 95% CI will be presented in the tables. The SAS code above will also be amended appropriately to obtain the right comparisons.

All figures, summaries and analyses will be performed on the FAS.

The data will be presented in the below outputs, the TFL number refers to the TFL number in the accompanying TFL shell document:

TFL number	Title
FIGURES	
15.1.2.35	MNWS Total Scores Arithmetic Mean and 95% CI – FAS
15.1.2.36	MNWS Total Scores Arithmetic Least Squares Means and 95% CI – FAS
TABLES	
15.2.4.46	Descriptive Statistics of MNWS Total Scores – FAS
15.2.4.47	Analysis of MNWS Total Scores – FAS

TFL number	Title
LISTINGS	
15.3.6.12	Listing of MNWS Questionnaire Results and Changes from Baseline

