 - THS 2.2 Arm: 80 subjects, ad libitum use of the product.
 - CC Arm: 40 subjects, ad libitum use of their preferred CC brand.
 - SA Arm: 40 subjects who will abstain from smoking.

Subjects will be informed of their randomized study arm by the study site staff on Day 1 prior to 06:30 AM.
- Exposure period (from Day 1, 06:30 AM until Day 5, 11:00 PM):

The exposure period will consist of 5 days of ad libitum use of the assigned product between 06:30 AM and 11:00 PM in THS 2.2 and CC arms. Use of any tobacco/nicotine-containing product other than the assigned product will not be allowed and may, at the discretion of the Investigator or designee, result in the subject withdrawal from the study.

Subjects in the SA arm will be asked to abstain from smoking any nicotine/tobacco-containing product and will not be provided with medication to support SA.

The end of the 24-hour urine collection period for Day 5 will end in the morning on Day 6 prior to Discharge.
- Day of Discharge (Day 6) (from Day 5, 11:01 PM to time of Discharge):

Procedures of Discharge, including but not limited to laboratory parameters, will be conducted to discharge the subject from the clinic after 9 days in a confined setting. Use of CC will be allowed on Day 6, but only after spirometry has been performed.
- Safety follow-up period (from Day 6, time of Discharge to Day 13):

Confidentiality statement: Data and information contained in this document are considered to constitute trade secrets and confidential commercial information, and the legal protections provided to such trade secrets and confidential information are hereby claimed under the applicable provisions of applicable law. No part of this document may be publicly disclosed without the written consent of Philip Morris Products S.A.

After time of Discharge, subject will enter a 7-day safety follow-up during which there will be recording of spontaneously reported new AEs/SAEs and the active follow-up of ongoing AEs/SAEs by the study site. In general, all AEs will be actively followed until resolved, stabilized (i.e., no worsening of the event), or a plausible explanation for the event has been found. The end of study (EOS) is defined as the time of Discharge on Day 6 plus 7-day follow-up period.

During the study, subjects in the CC and THS 2.2 arms who want to quit smoking will receive appropriate medical advice and will be referred to a smoking cessation counselor.

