7.8.4.5 Minnesota Nicotine Dependence/Withdrawal Scale (revised version)

The MNWS is a valid and reliable scale that has been used previously to examine signs and symptoms of withdrawal from cigarette smoking (Hughes and Hatsukami, 1986; Hughes and Hatsukami, 2008). It consists of two scales: a 'self-report scale' and an 'observer scale'.

For the purpose of this study, only the self-reporting scale will be used and filled-in by the subject. Furthermore, the subject's weight will not be recorded for the purpose of the MNWS. At the end of the assessment of the questionnaire, the subject's pulse rate will be recorded.

Subjects will be asked to rate the items for the previous 24-hours on a scale ranging from 0 to 4 (where 0 = none, 1 = slight, 2 = mild, 3 = moderate, 4 = severe).

The MNWS (revised version) will be completed on a daily basis from Day 0 to Day 6. On each day, MNWS has to be asked prior to product use.

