9.2.3 Exposure Period (Days 1 to 5)

The tables in this section show the assessments that will be performed during the confinement period (Day 1 to Day 5). Table 10 shows the assessments that will be performed on Day 1:

Table 10. Time Schedule - Day 1

| Time | Blood sample | Procedures | Additional information |
|---------------------------|--------------|---|--|
| Start of procedure | | Day 1 | |
| | | AE/SAE recording; concomitant medication | All day |
| | | Support during smoking abstinence (SA arm only) if needed | All day |
| 6:29 AM +/-30 min | | Analysis sample to be taken after final portion of urine has been added to Day 0 sampling bottle. Must be prior to first product use of Day 1 | BoExp, creatinine, and Ames mutagenicity in 24-hour urine Risk markers: 8-epi-PGF2 α and 11-DTX-B2 Bio-banking for BoExp/ risk markers in 24-hour urine (if additional consent is obtained) |
| 6:30 AM +/-30 min | | Start collection to Day 1 sampling bottle | |
| | | Assessment of cough (VAS) | To be done prior to product use but no later than 10:00 PM |
| | | MNWS questionnaire | To be done prior to product use but no later than 10:00 PM |

Confidentiality statement: Data and information contained in this document are considered to constitute trade secrets and confidential commercial information, and the legal protections provided to such trade secrets and confidential information are hereby claimed under the applicable provisions of applicable law. No part of this document may be publicly disclosed without the written consent of Philip Morris Products S.A.

| Time | Blood sample | Procedures | Additional information |
|--------------------------------|--------------|---|--|
| Start of procedure | | Day 1 | |
| | | CO breath test | To be done within 15 minutes prior first product use (for THS 2.2 and CC arms) or 08:00-10:00 AM (SA arm) |
| 6:30 AM | | Beginning of product use | |
| 06:30 AM-11:00 PM | | HST | In THS 2.2 and CC arms, HST SODIM [®] device has to be used for all product uses if compatible CCs are smoked |
| Before 10:00 AM | | Breakfast | |
| 10:00 AM-12:00 PM | | Vital signs (blood pressure, pulse rate, respiratory rate) | At least 5 minutes in supine position prior to measurement |
| 12:00 PM-02:00 PM | | CO breath test | |
| before 03:00 PM | | Lunch | |
| 04:00 PM-06:00 PM | | CO breath test | |
| afternoon | | Snacks | |
| In the evening before 09:00 PM | | Dinner | |
| 08:00 PM-10:00 PM | | CO breath test | |

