12.1.2 Definitions for Statistical Data Analysis

In general, baseline is the last available time-point prior to Day 1, 06:30 AM.

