S-PMA	S-phenylmercapturic acid
THS	Tobacco Heating System
TFL	Tables, Figures, and Listings
t_{peak}	Time to peak concentration
ULOQ	Upper Limit of Quantification
UV	Ultra violet
VAS	Visual Analogue Scale
WHO	World Health Organisation
YG1024+S9	Ames Mutagenicity Test

The following special terms are used in this SAP:

Baseline period	06:30 AM at Day -1 until 06:29 AM of Day 1 (and prior to product use /CC consumption on Day 1 if randomized to THS 2.2 or CC arm).
Conventional cigarette (CC)	The term 'conventional cigarette' refers to manufactured and commercially available cigarettes and excludes hand-rolled cigarettes, cigars, pipes, bidis, and other nicotine-containing products.
CC incompatible with Human Smoking Topography (HST) device	All CCs that are incompatible with the HST device (e.g., slim CC).
Day of Discharge	Day 6
Enrolment	On Day -2 for eligible subjects after all applicable inclusion and exclusion criteria have been satisfactorily met and the subject is willing and ready to use THS 2.2 (the test of THS 2.2 is the last assessment prior to enrolment).
Exposure period	06:30 AM of Day 1 until 11:00 PM of Day 5
Randomization	Assignment of the subject randomization number in the Interactive Web and Voice Response System (IXRS). This can be done any time on Day 0, however, subjects are not informed of their randomization group and number prior to Day 1.
Run-in period	Admission to site until 06:29 AM of Day -1
Safety follow-up	After the time of Discharge, a 7-day safety follow-up will be done for the recording of spontaneously reported new AEs/SAEs and the active follow-up of ongoing AEs/SAEs by the site.
Screening failure	Subjects who are not enrolled will be considered a screening failure and will be replaced by other subjects.
Tobacco Heating System 2.2 (THS 2.2)	THS 2.2 is comprised of the following components: Tobacco Stick, Holder, Charger, a Cleaning Tool, a mains power supply, and a USB cable.

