7.3.4 Minnesota Nicotine Withdrawal Scale (revised edition) Questionnaire

The MNWS (Hughes and Hatsukami 2008) is a 24 hour recall that will be completed by the subject him/herself daily on Day 0 to Day 6 prior to product use to reflect the previous days experience. Therefore although it is collected on Days 0 to 6 it will be reported as Days -1 to 5. Only the self-reported part of the MNWS will be used.

The self-reported part of the MNWS consists of the following 15 items which are rated over the last 24 hours on a scale of 0 to 4 (see Table 6). Higher scores indicate greater intensity on that scale.

The total scores will be derived by summing the individual item scores if all items are non-missing, otherwise the total score will be set to missing. The first total score calculated by summing the first 9 items is based on validated items, the second score is

based on 6 extra items which are thought to have an impact on withdrawal but have not been validated.

Table 6: Minnesota Nicotine Withdrawal Scale (Revised Edition) Questionnaire Scores

	Question	Total Score
1	Angry, irritable, frustrated.	1 and 2
2	Anxious, nervous.	1 and 2
3	Depressed mood, sad.	1 and 2
4	Desire or craving to smoke.	1 and 2
5	Difficulty concentrating.	1 and 2
6	Increased appetite, hungry, weight gain.	1 and 2
7	Insomnia, sleep problems, awakening at night.	1 and 2
8	Restless.	1 and 2
9	Impatient.	1 and 2
10	Constipation	2
11	Dizziness	2
12	Coughing	2
13	Dreaming or nightmares	2
14	Nausea	2
15	Sore throat	2

If the baseline score is 0, the percent change from baseline will be calculated using a value of 1 for the denominator.

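### The clock-time baseline rule for the exploratory MNWS analysis does not fit a recall form completed on the morning the arm is disclosed

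*SAP*

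**What the plan says.** - **Baseline.** SAP 12.6.3.1.3: "The baseline will be the last assessment prior to 06:29 AM on Day 1". The protocol's general rule (12.1.2) reads "In general, baseline is the last available time-point prior to Day 1, 06:30 AM". The SAP's own term for the baseline period (section 4) runs "06:30 AM at Day -1 until 06:29 AM of Day 1 (and prior to product use", and the added condition is attached to the THS 2.2 and CC arms only.
- **Form.** Protocol 7.8.4.5: "Subjects will be asked to rate the items for the previous 24-hours on a scale ranging from 0 to 4", and "On each day, MNWS has to be asked prior to product use". SAP 7.3.4 then shifts the labels: "Therefore although it is collected on Days 0 to 6 it will be reported as Days -1 to 5".
- **Completion window.** For Day 1, protocol Table 10 (section 9.2.3) says "To be done prior to product use but no later than 10:00 PM". SAP Table 16 has the same 10:00 PM limit for Days 0 to 6. Protocol Tables 11 to 15 set 10:00 AM for Days 2 to 6.
- **Disclosure.** Protocol 4.1: "Subjects will be informed of their randomized study arm by the study site staff on Day 1 prior to 06:30 AM". Protocol Table 9 rules out telling subjects their arm on Day 0.
- **Use of the score.** In SAP 12.6.3.1.3 the baseline is a covariate in the repeated-measures ANCOVA, with THS 2.2-CC and THS 2.2-SA contrasts, and the reference for the change summaries. SAP section 9 makes the comparison over all time points the main one.

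**The concern.** A baseline should be measured before the subject can react to the allocation, and on the same day for everyone. The MNWS rule guarantees neither. The scale asks about anger, anxiety, low mood and craving, and the trial is open-label. A subject who has just been told to abstain may rate those items differently even though the recall period is the day before. If that score is the covariate, part of any arm difference can be adjusted away. If instead the clock decides, the minute at which a form was filled in decides which day is the baseline, and a form describing the last day of own-brand smoking can enter the comparison as if it were a response to the assigned regimen.

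**Working it through.** No sample size, power or alpha figure is involved. The check is a comparison of times.

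**Step 1. What each form describes (SAP 7.3.4; protocol 7.8.4.5, Table 9 and 4.1)**

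| Form completed | Reported as | Recall covers | Arm known at completion? |
|---|---|---|---|
| Day 0 | Day -1 | Day -1, own cigarettes | No |
| Day 1 | Day 0 | Day 0, own cigarettes, if completed early | Not fixed |
| Days 2 to 6 | Days 1 to 5 | Exposure days | Yes |

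**Step 2. The morning of Day 1**

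- Baseline cut-off: 06:29 AM.
- Disclosure: some time before 06:30 AM.
- Product use opens: 06:30 AM.
- Outer limit for the form: 10:00 PM, which is 15 h 31 min after the cut-off.

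Neither document places the form before disclosure or before 06:29 AM. A late form is foreseeable: protocol section 9 says the listed times are for the first subject, and Table 10 also puts urine hand-over, cough assessment and a CO test into the same part of the morning. In the THS 2.2 and CC arms the form is bounded by first product use. SA subjects have no product use on Day 1, so 10:00 PM is their only bound.

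**Step 3. The two readings**

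- *(a) The reported day governs.* The Day 1 form (reported Day 0) is baseline for everyone. It may be completed before or after the subject learns the arm. In SA it may also cover time spent abstaining: a form completed h hours after 06:30 AM has h/24 of its recall window in the exposure period. At 10:00 AM that is 3.5/24 = 15%; at 10:00 PM it is 15.5/24 = 65%.
- *(b) The clock time of completion governs.* A Day 1 form completed before 06:29 AM is baseline, and may still follow disclosure. One completed at or after 06:29 AM is not, so the baseline falls back to the Day 0 form (reported Day -1) and the Day 1 form becomes post-baseline. Because the bound on completion differs by arm, so may the frequency of the fall-back.

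**Step 4. What each reading does to the analysis**

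- Under (a), if knowing the arm raises the mean SA baseline by d points relative to THS 2.2, the SA change from baseline is understated by d. With covariate slope b, the adjusted THS 2.2-SA difference moves by b × d. Neither b nor d is in the documents, and d may be zero.
- Under (b), reported Day 0 becomes a sixth time-point level beside Days 1 to 5. The model (code in SAP 12.6.3.1.1) has a product-by-time-point term, and least squares means for product weight the levels equally by default. The extra level would therefore carry 1/6 of the weight in the overall contrast, however few subjects supply it. The resulting bias depends on the arm difference at that level, which is unknown.

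**Step 5. Why only this questionnaire**

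The QSU-brief and MCEQ sections use the same baseline sentence, but SAP Table 16 has those forms completed between 08:00 PM and 11:00 PM. Their last assessment before 06:29 AM on Day 1 is the Day 0 evening form, before disclosure. The sentence works there and fails for a morning recall form.

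**The case against.** The best defence is that reading (a) is the natural one. SAP 12.6.3.1.3 speaks of forms given on Days 0 to 6 for the assessment of Days -1 to 5, the baseline period includes all of Day 0, and profiles are planned from baseline to Day 5. Read that way, no baseline moves between subjects and no sixth point appears. This is fair, and it means the two problems are alternatives that cannot be added together. It does not rescue the rule, because reading (a) leaves the form unordered against disclosure, and the sentence as written gives a clock time.

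The defence also notes that the form recalls a day when everyone was smoking, so any shift from disclosure would be a change in reporting, not withdrawal. That stands for forms completed early. It does not cover an SA form completed hours into Day 1.

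Finally, MNWS is exploratory, the protocol names it for Day 5 (section 3.4.3), and SAP section 9 plans estimates at each time point. A misplaced pre-exposure point would not be averaged into the Day 5 estimate. That also stands, although the Day 5 estimate is still adjusted for the baseline in question.

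A reader might go further and infer a definite bias, for example 0.5 to 2.1 points from a shift of 1 to 3 points and a slope of 0.5 to 0.7, or a 17% dilution in the affected subjects. The documents support neither. The first only multiplies assumed inputs and leaves out a zero shift. The second does not match a model whose product means average over time-point levels and not over each subject's own visits.

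**Conclusion.** The rule is defective as written, and the defect is confined to the exploratory MNWS analysis. Either the baseline may be scored after the subject knows the arm, or it falls on different days for different subjects and a mainly pre-exposure recall is counted as post-baseline. The size of either effect cannot be derived from the documents. It depends on when the forms were completed, when each subject was told the arm, and how far that knowledge changes recall ratings. It would be wrong to infer that the baseline has already been altered by allocation: the order of form and disclosure is left open, not set the wrong way round. The primary biomarker analysis does not use this score. Because a short rule removes the ambiguity, it is worth settling before database lock.

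**What to change.** In SAP 12.6.3.1.3, identify the baseline by form or reported day instead of clock time, for all subjects, and limit post-baseline points to reported Days 1 to 5 (forms of Days 2 to 6). Two choices are defensible:

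- **Day 0 form (reported Day -1) for everyone.** This is the only form certain to precede disclosure. The Day 1 form is then reported descriptively. The cost is a baseline one day further from the switch.
- **Day 1 form (reported Day 0), only where its recorded completion time precedes disclosure,** with the Day 0 form as the stated fall-back or sensitivity analysis. This keeps the last pre-exposure day, but needs the disclosure time on record, which neither document requires, and the fall-back leaves some subjects with an earlier baseline day.

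Either is SAP wording and a programming rule, with no new data. If the protocol can still be amended, Table 10 should also say that the Day 1 form is completed before disclosure. That would be a minor amendment, and under protocol section 1.1 all amendments go to the ethics committee. Moving the Day 1 limit from 10:00 PM to 10:00 AM would not be enough, since 10:00 AM is still after both disclosure and the 06:29 AM cut-off.
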